7.7. Pharmacokinetic Analyses

7.7.1. Pharmacokinetic Parameter Calculation Methods

Part 1

Pharmacokinetic parameters will be calculated by noncompartmental analysis method from concentration-time data using WinNonlin Professional (Version 5.2 or later) following these guidelines:

- Actual sampling times relative to study drug administration will be used for all calculations of the PK parameters. If there is any doubt as to the actual time a sample was taken, then the scheduled time will be used. Descriptive statistics will be used to summarize the PK parameters.
- There will be no imputation of missing data.

For the calculation of AUCs from PK concentrations, concentration below the limit of quantification (BLOQ) will be handled as follows:

- Pre-dose values will be set to zero.
- All remaining BLOQ values will be set to missing.

Pharmacokinetic parameters will be estimated according to the following guidelines:

- The maximum observed plasma concentration (C_{\max}) will be obtained directly from the concentration-time data.
- Time to maximum concentration (T_{\max}) is the time at which C_{\max} is observed.
- The apparent terminal elimination rate constant (λ_z) will be estimated at terminal phase by linear regression after log-transformation of the concentrations:
 - Only those data points that are judged to describe the terminal log-linear decline will be used in the regression.
 - A minimum number of three data points in the terminal phase will be used in calculating λ_z with the line of regression starting at any post- C_{\max} data point (C_{\max} should not be part of the regression slope) and including C_{last} , t_{last} .
 - The adjusted correlation coefficient (R^2 adjusted) in general should be greater than 0.90. Any value less than 0.90 may be used at the pharmacokineticist's best knowledge and judgment.
 - An appropriate number of decimal places should be used for λ_z to enable the reported value of half-life ($t_{1/2}$) to be calculated.
- Half-life ($t_{1/2}$) will be calculated as $\ln 2/\lambda_z$.
- AUC will be calculated as follows:
 - The linear trapezoidal method will be employed for all incremental trapezoids arising from increasing concentrations and the logarithmic trapezoidal method will be used for those arising from decreasing concentrations.
 - $AUC_{(0-t)} = \int_0^t C(t) dt$.
 - $AUC_{(0-\text{inf})} = \int_0^t C(t) dt + \int_t^{\infty} C(t) dt = AUC_{(0-t)} + C_t/\lambda_z$.
 - $C_{(t)}$ is last observed quantifiable concentration.

7.7.2. Pharmacokinetic Concentrations and Variables

The analysis of the PK data will be based on the PK analysis set.

Bupivacaine plasma concentrations will be listed by treatment group, subject, nominal time, and actual time. Concentrations that are BLOQ will be indicated by BLOQ in this listing.

Plasma concentrations will be summarized by treatment at each time point. The following descriptive statistics will be presented for plasma concentrations obtained at each nominal time point: n, geometric mean, arithmetic mean, SD, %CV, minimum, median, and maximum.

Pharmacokinetic parameters will be summarized by treatment. Descriptive statistics for calculated PK parameters will include: n, arithmetic mean, SD, %CV, geometric mean, median, minimum and maximum values. Geometric mean will not be presented for T_{\max} . Values of %AUC extrapolated > 20% will be flagged in the listings.

Individual plasma concentration versus actual times will be plotted by treatment in linear and semi-logarithmic scale.

At the 15 minute time point, unbound bupivacaine will be evaluated. The percentage of unbound over the total (unbound/total*100) will be summarized for subjects who have both values.

7.8. Safety Analyses.

All summaries of the safety data will use the safety analysis set.

7.8.1. Adverse Events

All AEs will be coded and summarized by system organ class (SOC) and preferred term based on the Medical Dictionary for Regulatory Activities (MedDRA) coding dictionary.

An AE will be considered treatment-emergent if the onset is any time on or after study drug administration through Day 30.

Only treatment-emergent AEs (TEAEs) that were not solicited from the Neurological Assessment or from the Opioid-Related Adverse Event Questionnaire will be summarized in the tables. All other AEs, those that occur after randomization but prior to study drug administration, AEs that occur after Day 30, or AEs that were solicited from the Neurological Assessment or from the Opioid-Related Adverse Event Questionnaire will appear in listings only.

Tables of AEs will show Part 1 and Part 2 data separately and combined.

Treatment-emergent AEs will be summarized [n (%)] and grouped by SOC and preferred term for each treatment group and for all subjects. If a subject experiences more than one episode of a particular TEAE, the subject will be counted only once for that event at each level of summarization (overall, by SOC, and by preferred term).

Similarly, TEAEs will be summarized in terms of maximum severity ('Mild', 'Moderate', and 'Severe'), study drug related TEAEs, and serious AEs.

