12.6. Safety Endpoints

The following safety endpoints will be assessed based on the safety measurements conducted at the specified time points:

- Incidence of TEAEs and SAEs through Day 30.
- Change from baseline in vital signs (resting heart rate and blood pressure) at each assessed time point.
- Summary of neurological assessments (proportion of subjects who are oriented, and proportion of subjects who have any of the neurological events).
- Change from baseline in ECG data closest to the median T_{max} .

- Proportion of subjects able to walk 20 meters, unassisted, at 24 hours, 72 hours, and on Day 30.
- Rating of physician satisfaction with return of sensory/motor function at 72 hours and Day 30.

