14.1. Adverse Events

14.1.1. Definitions

Definition of Adverse Event (AE): Any untoward medical occurrence associated with the use of a drug in humans, whether or not considered drug related. An AE (also referred to as an adverse experience) can be any unfavorable and unintended sign (e.g., abnormal laboratory finding), symptom, or disease temporally associated with the use of a drug, without any judgment about causality. An AE can arise from any use of the drug (e.g., off-label use in combination with another drug) and from any route of administration, formulation, or dose, including an overdose.

An AE can be any unfavorable and unintended change in a body structure or body function. Adverse events include any clinically significant deterioration of a subject's medical status. The AE may involve any organ or system and can be represented by the new onset or deterioration of a disease, a syndrome, a symptom, a physical sign, as well as by findings and results of instrumental examinations and laboratory tests. Any medically relevant and untoward change after the subject is randomized, including frequency or pattern changes for a fluctuating condition (e.g., migraine) is considered an AE.

An AE that occurs after randomization and before the start of the study drug administration is identified as a pretreatment AE (PTAE). An AE that occurs after the administration of the study treatment is considered a TEAE. All AEs must be recorded and reported accordingly, whether they appear causally related to the study drug or not. Adverse events will be followed until the outcome is known or until the end of the study.

Definition of Adverse Reaction: Any AE caused by a drug. Adverse reactions are a subset of all suspected adverse reactions for which there is reason to conclude that the drug caused the event.

Definition of Suspected Adverse Reaction: Any AE for which there is a reasonable possibility that the drug caused the AE. For the purposes of IND safety reporting, 'reasonable possibility' means there is evidence to suggest a causal relationship between the drug and the AE.

A suspected adverse reaction implies a lesser degree of certainty about causality than adverse reaction, which means any AE caused by a drug. Suspected adverse reactions are a subset of all AEs for which there is a reasonable possibility that the drug caused the event.

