15.6.5.1 Adverse Events

Adverse events from Part 1 and Part 2 will be shown separately and combined.

Adverse event verbatim terms will be mapped to preferred terms and related system organ class using the Medical Dictionary for Regulatory Activities (MedDRA). All summaries of AEs will only include TEAEs. Events that start prior to the start of study drug administration will be identified in listings only. Incidence rates of TEAEs and the proportion of subject prematurely withdrawn from the study due to a TEAE will be shown for each treatment group. Incidence rates also will be displayed for each treatment group for study drug-related TEAEs and by severity. Incidence rates of SAEs also will be shown for each treatment group. All incidence rates will be categorized and displayed by system organ class and preferred term.

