Appendix 2: Neurological Assessment

A neurological assessment will be conducted at baseline, 15 minutes, 30 minutes, and 1, 2, 4, 8, 12, 18, 24, 30, 36, 42, 48, 60, and 72 hours after surgery.

The examination will include the subject's orientation.

- Is the subject oriented? Yes No Not Assessable

Additionally, the subject will be asked the following questions:

- Do you have numbness of the lips, the tongue, or around the mouth? Yes No
- Do you have a metallic taste in your mouth? Yes No
- Are you having problems with your hearing? Yes No
- Are you having problems with your vision? Yes No
- Are your muscles twitching? Yes No

If the subject answers "yes" to any of these questions, the event should be recorded as an AE.

If the neurological assessment reveals a neurological event that the Investigator believes may be associated with high levels of systemic bupivacaine, an unscheduled PK blood sample should be collected at the time that the event is noted.

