Appendix 6: Opioid-Related Adverse Events Questionnaire

The opioid-related adverse events questionnaire will be completed at 72 hours after surgery during Part 1 only. The subject will be asked the questions below.

Since your operation, have you had:

[figure not shown]
- Itching all over your body? Yes No
- Excessive tiredness? Yes No
- Difficulty breathing? Yes No
- Did you need a postsurgical bladder catheter? Yes No
- Vomiting? Yes No
- Need for medicine to prevent vomiting? Yes No
- Constipation? Yes No
- Confusion? Yes No
- Delirium? Yes No

If the subject answers "Yes" to any of these questions, the event should be recorded as an AE.

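### SAP 7.8.1 keeps adverse events solicited by questionnaire, even serious ones, out of the TEAE and SAE tables that the protocol requires

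*SAP*

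**What the plan says.** SAP 7.8.1 sets the rule for the adverse event tables: "Only treatment-emergent AEs (TEAEs) that were not solicited from the Neurological Assessment or from the Opioid-Related Adverse Event Questionnaire will be summarized in the tables". Solicited events join pre-dose and post-Day 30 events in the listings. The summaries by severity, relatedness and seriousness follow in the same section with no exception.

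The protocol is wider. Section 14.1.1: "An AE that occurs after the administration of the study treatment is considered a TEAE". Section 12.6 names as a safety endpoint "Incidence of TEAEs and SAEs through Day 30". Section 15.6.5.1 asks for TEAE incidence overall, by severity and for related events. It adds that "the proportion of subject prematurely withdrawn from the study due to a TEAE will be shown for each treatment group", and also: "Incidence rates of SAEs also will be shown for each treatment group". Its only listings-only rule concerns timing: "Events that start prior to the start of study drug administration will be identified in listings only".

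Both instruments generate adverse events. Appendix 2 says of a yes answer "to any of these questions, the event should be recorded as an AE", and Appendix 6 gives the same instruction for the ORAE questions. They differ in reach. Protocol 13.5 puts the neurological assessment under Parts 1 and 2 on one schedule, whereas Appendix 6 says: "The opioid-related adverse events questionnaire will be completed at 72 hours after surgery during Part 1 only".

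**The concern.** The SAP selects events for the tables by how they were found, and the protocol does not. An event that the protocol records as an AE, classes as a TEAE and wants counted by arm can be absent from every TEAE and SAE table.

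This matters most for the neurological assessment. Protocol 9.2 gives it, with the cardiac assessment, the job of ruling out bupivacaine toxicity. If it finds a severe, related or serious event, a reader of the tables would see a yes answer at a time point but no incidence by those attributes. Because the exclusion has no exception for seriousness, the SAE table itself can be incomplete.

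**Working it through.** The plan states no figure on this point to reproduce. The check is a comparison of texts, with simple arithmetic for scope.

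1. **The two rules side by side**

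| Question | Protocol 14.1.1, 12.6, 15.6.5.1 | SAP 7.8.1 |
|---|---|---|
| What is a TEAE? | Any AE after study treatment | Onset on or after study drug, through Day 30 |
| Which TEAEs are tabulated? | All | Unsolicited only |
| What goes to listings only? | Pre-dose events | Pre-dose, post-Day 30 and all solicited events |
| Exception for serious, severe, related or discontinuation-causing events? | Not needed | None |

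The post-Day 30 item is not a material conflict, because the protocol endpoint also ends at Day 30. The solicited item is the conflict.

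2. **One event traced through.** Suppose a Part 2 subject answers yes to muscle twitching at 2 hours, and the event is judged serious and related.
   - By the protocol it is an AE, a TEAE and an SAE. It should count in incidence overall, by severity, among related events and among SAEs.
   - By SAP 7.8.1 it enters none of Tables 14.3.1.1-2 to 14.3.1.5-2.
   - It does appear as a yes in Table 14.3.3-2 and in Listings 16.7.1.1 to 16.7.1.4. If an unscheduled PK sample was drawn, it is also in Listing 16.6.3.
   - No table shows it by seriousness, severity, relationship or MedDRA term.

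3. **Are serious events exempt by implication?** The last sentence of 7.8.1 mentions serious AEs, but it extends the TEAE summary just described and states no exemption. The shell for Listing 16.7.1.3, the SAE listing, has source columns for both instruments. A serious solicited event is therefore foreseen and has a listing but no table.

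4. **Scope by part**
   - Neurological symptom questions (Appendix 2): 5. Post-surgery time points (15 and 30 minutes, then 1, 2, 4, 8, 12, 18, 24, 30, 36, 42, 48, 60 and 72 hours): 15. Answers per subject: 5 × 15 = 75, in both parts.
   - ORAE items (SAP 7.6.1): 9, asked once, in Part 1.
   - Solicited items: 5 + 9 = 14 in Part 1 and 5 in Part 2.

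5. **Weight of one subject.** If a subject's only event in a table row is excluded, that row falls by 1/25 = 4.0 points in a planned Part 1 arm and 1/90 = 1.1 points in a planned Part 2 arm. In a combined 266 mg or placebo arm the step is 1/(25 + 90) = 1/115 = 0.9 points. These are step sizes, not estimates of effect.

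**The case against.** The best defence is that the SAP only separates solicited from spontaneous reports, and that little is lost. Neurological events have their own safety endpoint (protocol 12.6) and analysis (15.6.5.5). The ORAE questionnaire is listed under efficacy assessments (12.1). The SAP tabulates both by arm, in Tables 14.3.3 and 14.2.2.15-1. Discontinuations for adverse events and deaths are in the disposition tables. A suspected toxicity event calls for an unscheduled PK sample, listed with its reason. SAE reporting to the sponsor (14.2.2) does not depend on how the event was found.

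Much of this stands. For routine non-serious yes answers, repeating the counts by system organ class is largely a matter of preference. Keeping a questionnaire used only in Part 1 out of combined rows is sensible. What does not stand is the idea that those outputs replace the protocol's tables. Tables 14.3.3 and 14.2.2.15-1 carry no seriousness, severity or relationship. The second uses the efficacy set by randomized treatment, whereas protocol 15.6.5 bases safety analyses on actual treatment.

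Three stronger readings are tempting and are not supported:

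- **The dose selection committee was denied neurological data.** SAP 7.9 lists one AE table and neither symptom table. But protocol 9.1 and 15.8 give the committee's review as a minimum that includes safety data. The SAP already names the selected dose, and the version in force at selection is not among the documents. What the committee saw cannot be stated.
- **The rule creates a mismatch with disposition.** The AE overview and the disposition table can disagree on discontinuations, but not only because of this rule. Disposition covers all randomized subjects and any AE; the overview covers treated subjects and TEAEs.
- **All ORAEs belong in the combined tables.** Only Part 1 subjects were asked, and spontaneous reports of the same terms in Part 2 are counted at an unknown rate. Dividing Part 1 questionnaire events by combined denominators would not give an interpretable rate.

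**Conclusion.** The conflict holds on the text. SAP 7.8.1 excludes by source, without exception, events that protocol 14.1.1, 12.6 and 15.6.5.1 require to be tabulated. It reaches neurological events in both parts and ORAEs in Part 1 only. The loss is limited to tabulated incidence of solicited events by seriousness, severity, relatedness and MedDRA term; the events remain in the listings.

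A reader might infer that toxicity signals are hidden or that a treatment comparison is biased. The documents support neither. The counts and listings exist, and the number of affected subjects and their split by arm cannot be derived. Confidence is high for the inconsistency and low for its numerical impact. It should be corrected because the plan as written can yield incomplete protocol safety tables and the repair is cheap.

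**What to change.** Amend SAP 7.8.1 as follows.

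1. Count every treatment-emergent SAE and every TEAE leading to discontinuation in the matching tables and in the any-TEAE row, whatever its source.
2. Include TEAEs solicited by the neurological assessment in Tables 14.3.1.1 to 14.3.1.5, both parts and combined, split into solicited and unsolicited by the flag in Listings 16.7.1.1 and 16.7.1.3. The schedule is the same in both parts, so pooling is sound.
3. Tabulate all other questionnaire-solicited ORAEs, of any grade or relatedness, in one separate Part 1 safety-set table by system organ class and preferred term, severity and relatedness. Leave them out of the Part 1 and combined any-TEAE and SOC/preferred-term rows. Do not admit them by grade or relatedness: SAP 7.1.3 sets missing severity to severe and missing relationship to related, so incomplete records could enter by imputation.
4. Treat an event that is both solicited and separately reported as unsolicited. The documents give no rule, and items 2 and 3 depend on one.
5. Footnote each shell with the sources counted. State that ORAE terms were asked about in Part 1 only, so combined rows for those terms mix two ascertainment rules.

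Item 3 still departs from protocol 15.6.5.1, but openly and with every attribute tabulated. The cost is SAP wording, footnotes, one added table and some programming; no new data are needed. TEAE percentages may rise in all arms, including placebo.

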7.8.2. Laboratory Parameters

Not applicable.

7.8.3. Vital Signs

Descriptive summaries of actual value and changes from Baseline will be calculated for systolic blood pressure, diastolic blood pressure, and heart rate. These summaries will be presented by treatment group at each time point for Part 1 and Part 2 separately and combined.

7.8.4. Other Safety Parameters

Neurological Assessments

The proportion of subjects who are oriented will be summarized by treatment group at each time point, for Part 1 and Part 2 separately and combined. Subjects who were 'not assessable'

will not be included in the calculation of the proportion. The proportion of subjects who have at least one of the neurological events and the proportion of subjects who have each of the neurologic events will be summarized by treatment group, for Part 1 and Part 2 separately and combined.

20-Meter Walk Test

The proportion of subjects able to walk 20 meters, unassisted, with the optional use of a four-legged walker, will be summarized by treatment group for Part 1 and Part 2 separately and combined. For Part 2, the proportion in the liposome bupivacaine group will be compared to placebo using a chi-square test.

Physician's Satisfaction with Return of Sensory/Motor Function

The physician will rate his/her satisfaction with return of sensory/motor function as Extremely dissatisfied, Dissatisfied, Neither satisfied nor dissatisfied, Satisfied, or Extremely satisfied at 72 hours and on Day 30. The categories will be summarized by treatment group at each time point for Part 1 and Part 2 separately and combined. For Part 2, a Wilcoxon Rank Sum test will be used to compare liposome bupivacaine to placebo.

Transfusions

The proportion of subjects who had a transfusion (after study drug administration) will be summarized by treatment group for Part 1 and Part 2 separately and combined. To determine if a subject had a transfusion a review of the concomitant medications will be done. Medications such as Packed Red Blood Cells will indicate that a subject had a transfusion.

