9.2. Discussion of Study Design

Liposome bupivacaine is approved for infiltration into a surgical wound. This multicenter, randomized, double-blind, parallel-group study is a comparison of the efficacy and safety of liposome bupivacaine to placebo when administered as a femoral nerve block in subjects undergoing unilateral TKA. The double blind study design is intended to avoid potential bias resulting from subject or Investigator knowledge of the assigned treatment.

Total knee arthroplasty is a frequently performed surgical procedure that causes postsurgical pain of considerable intensity and duration. Standard analgesia following TKA often includes IV and PO opioids postoperatively. Therefore, TKA was selected as an appropriate pain model for investigating a sustained-release formulation of bupivacaine, which has the potential to overcome the limitation reported in previous studies with regard to the duration of the analgesic effect obtained with commercially-available products.

During Part 1, subjects will receive a single dose femoral nerve block with one of three dose levels of liposome bupivacaine (67, 133, or 266 mg). An unblinded dose selection committee will review study data, determine the apparent efficacy and safety of each of the three liposome bupivacaine dose levels tested, and recommend a dose level to be tested during Part 2 of the study. In Part 2 of the study, subjects will receive a single dose injection femoral nerve block with the selected dose of liposome bupivacaine (i.e., 67, 133, or 266 mg) or placebo.

All subjects will receive an opioid (morphine, hydromorphone, and/or oxycodone) and conventional bupivacaine HCl, as needed, to control breakthrough postsurgical pain.

Neurological and cardiac assessments will be conducted to rule out bupivacaine toxicity related to high plasma exposure. Additionally, sensory and motor function assessments will be conducted in order to test for restoration of nerve function.

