13.1. Instructions for Conducting Procedures and Measures

With the exception of the PK assessments (which will be conducted after the beginning of study drug administration), all assessments conducted after baseline will be timed from the end of surgery. Day 1 is defined as the day on which study drug is administered. The beginning of surgery is defined as the time of the first incision. The end of surgery is defined as the time of the last suture/staple. Postsurgical is defined as after the end of surgery.

Subjects will be hospitalized for at least 72 hours after surgery; therefore, postsurgical analgesia and collection of study data through the primary endpoint will take place under the supervision of study staff.

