13.1.3. Neurological Assessment

A neurological assessment will be conducted at baseline, 15 minutes, 30 minutes, and 1, 2, 4, 8, 12, 18, 24, 30, 36, 42, 48, 60, and 72 hours after surgery. The examination will include the subject's orientation. Additionally, the subject will be asked whether s/he is experiencing any numbness and tingling of the mouth and lips, a metallic taste, blurred vision, tremors, or twitching (see [Appendix 2](#)). If the neurological assessment reveals a neurological event that the

Investigator believes may be associated with high levels of systemic bupivacaine, an unscheduled PK blood sample should be collected at the time that the event is noted.

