14.1.2. Recording Adverse Events

It is the responsibility of the Investigator to document all AEs (i.e., PTAEs and TEAEs) with an onset after the subject is randomized. For the purpose of this study, all AEs that occur through Day 30 after surgery must be recorded regardless of whether or not they are considered related to study drug. Whenever feasible, AE terms should be documented as medical diagnoses (highest possible level of integration); otherwise, the AEs should be reported separately as individual signs or symptoms. Only one AE per line should be recorded in the AE CRF; for example, an AE of nausea and vomiting should be listed as two separate events: the event of nausea and the event of vomiting. If a diagnosis is established after symptoms are recorded on the AE CRF, the diagnosis should be recorded and the symptoms collapsed (removed; i.e., lined through and initialed). Whenever possible, abnormal laboratory results should be reported as their clinical corollary (e.g., low potassium should be recorded as hypokalemia).

All AEs will be followed through progression and regression of their severity. For example, if an AE is reported as mild in severity but changes to moderate, the AE of mild will have an outcome of changed AE characteristic and the AE will be re-entered. The AE with a moderate severity must have the same start date as the mild event stop date. If the AE then becomes mild, the AE with a moderate severity will have an outcome of changed AE characteristic and the AE will be re-entered with a severity of mild; the start date of the mild AE must be the same as the stop date of the moderate AE.

Any condition noted before the subject is randomized will be listed as Medical History and is considered a pre-existing condition. If a pre-existing condition changes (i.e., becomes more severe or more frequent), at any time after randomization, or after study drug administration, it is considered an AE. Note: A change in treatment for a pre-existing condition (e.g., new high blood pressure medication), does not necessarily indicate an AE.

Information recorded on the AE CRF will include the AE term, the date and time of onset, severity, seriousness, relationship to study drug, action taken with study drug, action taken for the AE, and the outcome of the AE, including the date and time of resolution, if applicable.

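### The neurological safety summary has no new-onset definition, although a pre-dose baseline questionnaire is collected

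*SAP*

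**What the plan says.** Protocol 9.2 gives the purpose: "Neurological and cardiac assessments will be conducted to rule out bupivacaine toxicity related to high plasma exposure". The instrument is the questionnaire in Appendix 2. It is completed at baseline, before study drug (protocol 13.3), and at 15 time points from 15 minutes to 72 hours after surgery (13.1.3).

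The hearing and vision items ask about present status, not change, for example "Are you having problems with your hearing". Appendix 2 adds that if the subject answers yes "to any of these questions, the event should be recorded as an AE". Protocol 14.1.2 says: "Any condition noted before the subject is randomized will be listed as Medical History and is considered a pre-existing condition". Under that section such a condition becomes an adverse event only if it changes after randomization.

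SAP 7.8.4 will summarise "The proportion of subjects who have at least one of the neurological events", and the proportion with each event, by treatment group. The shells of Tables 14.3.3-1 and 14.3.3-2 have one block per time point, including a Baseline block, with a row for any event and a row for each item. SAP 7.8.1 sends adverse events solicited from this questionnaire to listings only.

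The two symptom lists differ. Protocol 13.1.3 has the subject asked about "experiencing any numbness and tingling of the mouth and lips, a metallic taste, blurred vision, tremors, or twitching". Appendix 2 and the table shells have no tingling or tremor item but do have a hearing item.

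**The concern.** The plan collects the information needed to separate new symptoms from old ones and then does not use it. By contrast, SAP 7.8.3, immediately before, summarises change from baseline for vital signs. For neurological symptoms a yes is a yes, whatever the subject answered before dosing. A subject with long-standing hearing loss can count as having a neurological event at all 15 postsurgical visits.

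The table is meant to show an excess of toxicity symptoms on active drug. Complaints that were present before dosing add a similar number of events to both arms and noise to the comparison. Because solicited events are kept out of the TEAE tables, no other planned table would show the excess more cleanly.

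**Working it through.** **1. What enters the count.** Protocol 12.6, protocol 15.6.5.5 and SAP 7.8.4 contain no restriction to new onset, to post-dose time points, or to subjects negative at baseline. In SAP 7.8.4 the orientation summary is tied to each time point. The sentence on neurological events is not, so it can be read as a per-subject proportion. The shells give only by-time rows. The text therefore leaves open which time points count, and the shells offer no per-subject figure on either reading.

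**2. Size of the dilution.** The documents give no neurological event rate, no prevalence of pre-existing complaints and no power for this endpoint. Their only power figure (above 97% for the primary AUC) reproduces at about 97.5% and has no bearing here. What follows is an illustration.

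Inputs:
- n = 115 per arm, from the planned 25 in Part 1 plus 90 in Part 2, for 266 mg and for placebo.
- Assumed: a fraction b of each arm has a persistent hearing or vision complaint, and new symptoms arise in 6% (active) and 1% (placebo) of the others.

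Formulas:
- As written: P(any yes) = b + (1 − b)p.
- New onset only: P(new) = (1 − b)p.
- SE = √[P₁(1 − P₁)/115 + P₀(1 − P₀)/115].

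For b = 20%:
- As written: 0.20 + 0.80 × 0.06 = 0.248 and 0.20 + 0.80 × 0.01 = 0.208. The difference is 0.040, the SE is √[(0.1865 + 0.1647)/115] = 0.055, and the ratio is 0.7.
- New onset: 0.048 and 0.008. The difference is 0.040, the SE is √[(0.0457 + 0.0079)/115] = 0.022, and the ratio is 1.9.

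| b | As written, active vs placebo | Difference/SE | New onset, active vs placebo | Difference/SE |
|---|---|---|---|---|
| 10% | 15.4% vs 10.9% | 1.0 | 5.4% vs 0.9% | 2.0 |
| 20% | 24.8% vs 20.8% | 0.7 | 4.8% vs 0.8% | 1.9 |
| 30% | 34.2% vs 30.7% | 0.6 | 4.2% vs 0.7% | 1.7 |

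The absolute difference is the same in both columns. What changes is the noise around it and the relative contrast: at b = 20% the risk ratio is 24.8/20.8 = 1.19 as written and 4.8/0.8 = 6.0 for new onset.

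A second set of assumptions agrees. With 90 per arm and new onset of 10% versus 2%, the as-written ratio is 1.61, 1.30 and 1.18 at b = 10%, 20% and 30%. Among baseline-negative subjects it stays at 5.0.

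The model lets a subject with a pre-existing complaint contribute no new event. An item-level rule would still count a new metallic taste in someone with old hearing loss, so the gain may be somewhat understated.

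**3. Adverse event recording.** At a postsurgical visit, an unchanged pre-existing complaint is an adverse event under the Appendix 2 sentence and is not one under 14.1.2. The two instructions conflict.

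**4. Timing.** Apart from PK sampling, "all assessments conducted after baseline will be timed from the end of surgery", and dosing is 0 to 2 hours before surgery. If surgery lasts 1 to 2 hours (an assumption), the first post-dose questionnaire falls between 0 + 1 + 0.25 = 1.25 hours and 2 + 2 + 0.25 = 4.25 hours after dosing. By then three to five of the 12 scheduled post-dose PK samples in Part 1 have been drawn. The SAP uses one of those early samples: "At the 15 minute time point, unbound bupivacaine will be evaluated".

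**The case against.** The summary is descriptive and no test of neurological events is planned, so a difference/SE ratio changes no planned decision. The shells show each arm's Baseline rate beside every later one. Perioral numbness, metallic taste and twitching have their own rows, which hearing or vision complaints cannot mask. Randomization balances pre-existing complaints in expectation, and Listing 16.9 would let a reader derive new onset by hand. The assumed rates come from outside the documents.

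All of this stands, and it limits the point to dilution in a descriptive table. It does not remove the point. The any-event row is still affected, no planned output performs the derivation, and no other table carries these events. The conflict over adverse event recording has little effect on tabulated TEAEs, because solicited events are listed only.

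A reader might go further and infer that early toxicity will be missed because the questionnaire starts only after surgery. The documents do not support that. The form is completed before dosing; only its first post-dose use follows surgery. Between dosing and the end of surgery, adverse events are recorded from randomization, the Holter ECG runs continuously, and an unscheduled PK sample is drawn if a suspected toxic event is noted. Subjects under general anesthesia could not answer a questionnaire for much of that interval.

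**Conclusion.** The point holds as a missing definition. A pre-dose baseline is collected, the items ask about current status, and nothing in the protocol or SAP separates new symptoms from persistent ones or fixes the time points behind the any-event proportion. The effect is non-directional dilution of the placebo contrast in the only table that reports these symptoms. Under the first illustration (115 per arm, 10% to 30% pre-existing, 6% versus 1% new onset), the difference/SE ratio is 0.6 to 1.0 as written and 1.7 to 2.0 with a new-onset rule. Those rates are assumptions. If few subjects have pre-existing complaints, little is lost.

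On timing, the documents support only this: no questionnaire is scheduled between dosing and 15 minutes after surgery, and other safety recording partly covers that interval. Moving Part 2 questionnaires to a post-dose clock is not warranted. Scheduled PK sampling is in Part 1 only, so the move would not pair symptoms with scheduled concentrations, and it would mix two clocks in the combined table.

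**What to change.** In SAP 7.8.4 and Tables 14.3.3-1 and 14.3.3-2:
- Define a new neurological event as a post-dose yes on an item answered no at baseline.
- Add per-subject rows, over all post-dose time points, for at least one new event and for each new item.
- State the denominators and how a missing baseline answer is handled.
- Keep the existing by-time rows.

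This needs SAP text and programming on answers already collected, and it loses no information.

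In the protocol, reconcile the Appendix 2 recording instruction with 14.1.2, and reconcile the symptom lists in 13.1.3 and Appendix 2 (tingling and tremors in one, hearing in the other). Both are text changes that affect only subjects not yet enrolled. Adding items to the form partway through would make the instrument differ between Parts 1 and 2, which the safety tables combine. If that route is chosen, the combined table should footnote it.
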